Follow-up Period for All Arms

- Weekly Follow-up for Four (4) Weeks (+/- one day) from last dose of treatment
 - Assessment completed by Research Nurse. May be conducted by phone.
 - Review of symptoms
 - . Review of daily temperatures
 - Adverse events
 - Record standard of care treatments and/or procedures prescribed

Monthly Follow-up for Six (6) Months (+/- one week)

- Assessment completed by Research Nurse. May be conducted by phone.
- Review of symptoms
- Review of daily temperatures
- Adverse events
- Record standard of care treatments and/or procedures prescribed

2. Treatment Plan:

Dosage and Administration

Hydroxychloroquine sulfate 200 mg po TID X 10 days Arm 1:

Azithromycin 500 mg po on day one, followed by 250 mg po QD X 4 days

- Arm 2: Hydroxychloroquine sulfate 200 mg po TID X 10 days
- Arm 3: Placebo Days 1-6, following viral sampling on day 6
 - Hydroxychloroquine sulfate 200 mg po TID x 10 days

Dose Modification:

Hydroxychloroguine

- For grade 1 or 2 intolerability: allow patient to hold one dose and resume as tolerated without adjustment
- For grade 3 or 4 toxicity: hold one dose and resume at BID dosing to complete the original 10 days of dosing
- For second episode grade 3 or 4 toxicity: hold next dose and resume at once daily dosing to complete the original 10 days of dosing.

Hydroxychloroquine sulfate

One hydroxychloroquine sulfate tablet contains 200 mg of hydroxychloroquine sulfate, which is the equivalent to 155 mg base.

For this study, dosing will be 200 mg TID PC x 10 days with or without azithromycin (depending on randomization).

Take hydroxychloroquine sulfate tablets with a meal or a glass of milk when permissible.

Azithromycin

For this study, dosing will be azithromycin 2 x 250 mg (500 mg) on Day 1, followed by 1 x 250 mg daily x 4 (D2 thru 5) with HCQ 200 mg TID PC x 10 days beginning on Day 1 (depending on randomization).

Placebo

Arm 3 only. For this study, participants will be provided 30 placebo tablets to maintain the blind between Arm 2 and Arm 3. Dosing will be placebo tablet x 3 daily (D1 thru 6).

Concomitant Medications & Supportive Guidelines

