Development of Drug-Resistant Bacteria: Prescribing azithromycin in the absence of a proven or strongly suspected bacterial infection is unlikely to provide benefit to the patient and increases the risk of the development of drug-resistant bacteria.

Drug interactions: Nelfinavir, Warfarin.

Potential Drug-Drug Interaction with Macrolides: Interactions with digoxin, colchicine or phenytoin have not been reported in clinical trials with azithromycin. No specific drug interaction studies have been performed to evaluate potential drug-drug interaction. However, drug interactions have been observed with other macrolide products. Until further data are developed regarding drug interactions when digoxin, colchicine or phenytoin are used with azithromycin careful monitoring of patients is advised.

Availability: FDA approved; commercially available azithromycin will be supplied free of charge to all patients enrolled.

Generic name: Hydroxychloroquine sulfate

Commercial name: Plaquenil

For complete information please refer to the package inserts at http://dailymed.nlm.nih.gov/dailymed/Hydroxychloroquine

Chemical name: 7-Chloro-4-[4-[ethyl-(2-hydroxyethyl)amino]-1-methylbutylamino] quinolone

Source: Commercially available

C18H26CIN3O+H2SO4

Molecular Weight: 433.95

Hydroxychloroquine sulfate tablets, USP contain 200 mg hydroxychloroquine sulfate, equivalent to 155 mg base, and are for oral administration.

Pharmacokinetics: Following a single 200 mg oral dose of hydroxychloroquine sulfate to healthy males, the mean peak blood concentration of hydroxychloroquine was 129.6 ng/mL, reached in 3.26 hours with a half-life of 537 hours (22.4 days). In the same study, the plasma peak concentration was 50.3 ng/mL reached in 3.74 hours with a half-life of 2963 hours (123.5 days). Urine hydroxychloroquine levels were still detectable after 3 months with approximately 10% of the dose excreted as the parent drug. Results following a single dose of a 200 mg tablet versus I.V. infusion (155 mg), demonstrated a half-life of about 40 days and a large volume of distribution.

Mechanism of Action: The precise mechanism by which hydroxychloroquine exhibits activity against *Plasmodium* is not known. Hydroxychloroquine, like chloroquine, is a weak base and may exert its effect by concentrating in the acid vesicles of the parasite and by inhibiting polymerization of heme. It can also inhibit certain enzymes by its interaction with DNA.

Warnings:

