Ocular: Irreversible retinal damage has been observed in some patients who had received hydroxychloroquine sulfate. Significant risk factors for retinal damage include daily doses of hydroxychloroquine sulfate greater than 6.5 mg/kg (5 mg/kg base) of actual body weight, durations of use greater than five years, subnormal glomerular filtration, use of some concomitant drug products such as tamoxifen citrate and concurrent macular disease.

Cardiac Effects, including Cardiomyopathy and QT prolongation: Post-marketing cases of life-threatening and fatal cardiomyopathy have been reported with use of hydroxychloroquine sulfate as well as with use of chloroquine. Hydroxychloroquine sulfate prolongs the QT interval. Ventricular arrhythmias and torsades de pointes have been reported in patients taking hydroxychloroquine sulfate (see OVERDOSAGE). Therefore, hydroxychloroquine sulfate should not be administered with other drugs that have the potential to prolong the QT interval.

Worsening of psoriasis and porphyria

Proximal Myopathy and Neuropathy

Neuropsychiatric events, including suicidality

Hypoglycemia: Hydroxychloroquine sulfate has been shown to cause severe hypoglycemia including loss of consciousness that could be life threatening in patients treated with or without antidiabetic medications

General precautions: General: Use with caution in patients with gastrointestinal, neurological, or blood disorders, and in those with a sensitivity to quinine.

Hepatic/Renal Disease: Antimalarial compounds should be used with caution in patients with hepatic disease or alcoholism or in conjunction with known hepatotoxic drugs. A reduction in dosage may be necessary in patients with hepatic or renal disease, as well as in those taking medicines known to affect these organs.

Hematologic Effects/Laboratory Tests: Antimalarial compounds should be used with caution in patients with hepatic disease or alcoholism or in conjunction with known hepatotoxic drugs. Periodic blood cell counts should be performed if patients are given prolonged therapy.

Hydroxychloroquine sulfate should be administered with caution in patients having glucose-6-phosphate dehydrogenase (G-6-PD) deficiency.

Dermatologic Effects: Dermatologic reactions to hydroxychloroquine sulfate may occur and, therefore, proper care should be exercised when it is administered to any patient receiving a drug with a significant tendency to produce dermatitis.

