The package labeling does not provide as clear a percent incidence as modern labels since hydroxychloroquine is an old medication. The following Council for International Organizations of Medical Sciences (CIOMS) frequency rating is used, when applicable: Very common ≥ 10 %; Common ≥ 1 and <10 %; Uncommon ≥ 0.1 and < 1 %; Rare ≥ 0.01 and <0.1 %; Very rare < 0.01 %; Not known (frequency cannot be estimated from available data).

Blood and lymphatic system disorders

Not known: Bone marrow depression, anemia, aplastic anemia, agranulocytosis, leucopenia, and thrombocytopenia (see Warnings and Precautions, Hematologic).

Cardiac disorders

Not known: Cardiomyopathy, which may result in cardiac failure and in some cases a fatal outcome. Chronic toxicity should be considered when conduction disorders (bundle branch block/ atrioventricular heart block) as well as biventricular hypertrophy are found. Drug discontinuation may lead to recovery (see Warnings and Precautions, Cardiovascular, Drug Interactions, and Symptoms and Treatment of Over dosage). Hydroxychloroquine prolongs the QT, PR and/or QRS intervals which may lead to an arrhythmia. Ventricular arrhythmias and torsade de pointes have been reported in patients taking hydroxychloroquine (see Warnings and Precautions, Cardiovascular, Drug Interactions, and Symptoms and Treatment of Over dosage).

Ear and labyrinth disorders

Uncommon: ≥ 0.1 and < 1 %: Vertigo, tinnitus.

Not known: Hearing loss, including cases of irreversible hearing loss.

Eye disorders

Common: ≥ 1 and <10 %: Blurring of vision due to a disturbance of accommodation which is dose dependent and reversible (see WARNINGS AND PRECAUTIONS, Ophthalmologic).

Uncommon: ≥ 0.1 and < 1 %: Maculopathies, which may be irreversible. Retinopathy with changes in pigmentation and visual field defects (see Warnings and Precautions, Ophthalmologic). In its early form it appears reversible upon discontinuation of the drug. If allowed to develop however, there may be a risk of progression even after treatment withdrawal. Patients with retinal changes may be asymptomatic initially, or may have scotomatous vision with paracentral, pericentral ring types, temporal scotomas, abnormal color visions, reduction in visual acuity, night blindness, difficulty reading and skipping words. Corneal changes including edema and opacities. They are either symptomless or may cause disturbances such as halos around lights especially at night, blurring of vision,

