vision disturbances, or photophobia. They may be transient or are reversible upon discontinuation of therapy (see Warnings and Precautions, Ophthalmologic). Not known: Macular degeneration, which may be irreversible.

Gastrointestinal disorders

Very common: ≥ 10 %: Abdominal pain, nausea.

Common: Diarrhea, vomiting.

These symptoms usually resolve immediately upon reducing the dose or upon stopping the treatment.

Hepatobiliary disorders

Uncommon: ≥ 0.1 and < 1 %: Abnormal liver function tests.

Not known: Fulminant hepatic failure (see Warnings and Precautions, Hepatic/Biliary/Pancreatic).

Immune system disorders

Not known: Urticaria, angioedema, bronchospasm.

Metabolism and nutrition disorders

Common: ≥ 1 and <10 %: Anorexia (usually resolves immediately upon reducing the dose or upon stopping the treatment).

Not known: hypoglycemia (see Warnings and Precautions, Endocrine and Metabolism). Hydroxychloroquine may exacerbate porphyria (see Warnings and Precautions, General).

Musculoskeletal and connective tissue disorders

Uncommon: ≥ 0.1 and < 1 %: Sensori motor disorders.

Not known: Skeletal muscle palsies or skeletal muscle myopathy or neuromyopathy leading to progressive weakness and atrophy of proximal muscle groups. Depression of tendon reflexes, abnormal results of nerve conduction tests. Myopathy may be reversible after drug discontinuation, but recovery may take many months (see Warnings and Precautions, Musculoskeletal).

Nervous system disorders

Common: ≥ 1 and <10 %: Headache.

Uncommon: Dizziness.

Not known: Convulsions. Extrapyramidal reactions such as: akathisia, dystonia, dyskinesia, gait disturbance, tremor.

Psychiatric disorders

Common: ≥ 1 and <10 %: Affect lability. Uncommon: ≥ 0.1 and < 1 %: Nervousness. Not known: Psychosis, suicidal behavior.

Skin and subcutaneous tissue disorders

Common: ≥ 1 and <10 %: Skin rash, pruritus.

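### As written, the hydroxychloroquine dose-modification rule resumes drug after one held dose for any grade 3 or 4 toxicity, with no recovery condition, event-type exception or permanent stop in the visible text

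*Protocol*

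**What the plan says.** Protocol Section 1.3 A.2 (Treatment Plan, Dose Modification) has three lines, all for hydroxychloroquine.

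- **Grade 1 or 2.** One dose may be held. Dosing then resumes at the same dose, subject to tolerance.
- **First grade 3 or 4 event.** "For grade 3 or 4 toxicity: hold one dose and resume at BID dosing to complete the original 10 days of dosing".
- **Second grade 3 or 4 event.** "For second episode grade 3 or 4 toxicity: hold next dose and resume at once daily dosing", again to the end of the 10-day course.

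Nothing is said about a third episode, and these lines name no grading scale.

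The protocol also describes the reactions that it expects from this drug. The hydroxychloroquine warnings in Section 1.7 state: "Ventricular arrhythmias and torsades de pointes have been reported in patients taking hydroxychloroquine sulfate". The adverse event list in Section 4.7 A repeats this. Under immune system disorders that list gives "Not known: Urticaria, angioedema, bronchospasm", and under skin disorders it includes toxic epidermal necrolysis, Stevens-Johnson syndrome and DRESS. For cardiomyopathy and conduction disorders it says "Drug discontinuation may lead to recovery". For gastrointestinal symptoms it says "These symptoms usually resolve immediately upon reducing the dose or upon stopping the treatment".

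**The concern.** Stepping down from three tablets a day to two and then one is a sensible response to dose-related intolerance such as nausea. The grade 3 and 4 lines are not limited to that. They speak of toxicity in general, and they omit the tolerance condition that the milder line carries. A site following them to the letter would give more hydroxychloroquine to a patient who had just had a life-threatening reaction to it, without first establishing that the patient had recovered.

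The setting makes a clear written rule more important. Outpatients dose themselves at home, the daily nurse assessment may be by phone (Section 1.3 A.1), and the visible schedule in Appendix A has an electrocardiogram at screening only. If drug should be stopped, the investigator has to depart from the written rule and has no visible criterion for doing so.

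**Working it through.** The plan gives no statistical figure on this point. The check is a reading of the text, followed by simple dose arithmetic.

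**1. Is there a recovery condition, an exception or a stop elsewhere in the visible text?**

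- Sections 1.3 C.2 to C.4 refer to withdrawal from treatment, but only to set the follow-up period. They give no criterion for withdrawal.
- Section 1.7 B says that medication follows both the protocol and the treating investigator's instructions. This allows judgement but sets no stopping rule.
- Section 4.4 gives the patient a right to withdraw.
- The azithromycin warnings in Section 1.7 call for stopping that drug after an allergic reaction. This is not a hydroxychloroquine rule and does not cover arrhythmia.
- SAP Section 6.3 A concerns stopping or suspending the study, not one patient's drug.

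None of these supplies what the Dose Modification lines lack.

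**2. The dose ladder.** The tablet is 200 mg, and the starting dose is one tablet three times daily (Section 1.3 A.2).

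- Start: 3 × 200 = 600 mg/day.
- After the first grade 3 or 4 event: 2 × 200 = 400 mg/day.
- After the second: 1 × 200 = 200 mg/day.
- No step reaches 0 mg/day.

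**3. Tablets still directed after a first event.** Suppose that the event falls at the end of hydroxychloroquine Day d and that the held dose is the first twice-daily dose of the next day. Tablets already taken are 3d, and further tablets are 2 × (10 − d) − 1.

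| Event at end of Day | Already taken | Further tablets | Further dose |
|---|---|---|---|
| 1 | 3 | 2 × 9 − 1 = 17 | 3,400 mg |
| 3 | 9 | 2 × 7 − 1 = 13 | 2,600 mg |
| 5 | 15 | 2 × 5 − 1 = 9 | 1,800 mg |
| 9 | 27 | 2 × 1 − 1 = 1 | 200 mg |

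If the held dose is not counted against the twice-daily schedule, each count rises by one. A permanent stop gives 0 in every row.

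**4. A second event.** Take a first event at the end of Day 3 and a second at the end of Day 5. Tablets taken are 9 + (2 × 2 − 1) = 12. The rule then directs (10 − 5) − 1 = 4 more, or 800 mg.

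**5. Who is exposed to the rule.** At the target size in SAP Section 6.1, Arms 1 and 2 give 60 + 60 = 120 patients, and Arm 3 brings this to 150. If all 160 are accrued at 2:2:1, Arms 1 and 2 give 64 + 64 = 128, and the 32 in Arm 3 bring this to 160. The figures with Arm 3 are upper limits, because Section 1.3 A.1 starts hydroxychloroquine in that arm only if symptoms continue on Day 6.

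**The case against.** The strongest defence is that these lines were meant for tolerability. They sit under dose modification, open with intolerability and describe a dose ladder. On that view no clinician would apply them to torsades or Stevens-Johnson syndrome. The investigator's instructions also govern dosing, nurse contact and adverse event review are daily during treatment, and the exclusions screen out many higher-risk patients. Section 1.7 refers readers to the package inserts for full information. Text is missing from parts of Section 4.7 and from Section 6.3 B, where a stopping rule could sit.

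Much of this stands as a limit on what can be claimed. It makes automatic re-dosing less likely and leaves open that a stop is written somewhere not visible. It does not remove the instruction to resume, which is in full view and has no qualifier.

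Four stronger readings are tempting, and the documents support none of them.

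- **Patients will be re-dosed after such events.** The text permits this. It does not show that it would happen.
- **The rule contradicts the exclusions for prior drug reaction, drug-induced QTc prolongation or serious ventricular arrhythmia.** Eligibility rules and on-treatment rules serve different purposes. The exclusions show only how the plan regards these risks.
- **The 120 to 160 patients are expected events.** They are patients to whom the rule could apply. The documents give no rate for these events and mark their frequency as not known.
- **The half-lives show how little drug clears during one held dose.** Section 1.7 gives 22.4 days in blood and 123.5 days in plasma after a single dose. Both are long beside one held dose, but they say little about the early distribution phase or about harm from an allergic reaction. No figure here rests on them.

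**Conclusion.** The point holds as a patient-safety defect in the rule as written. The Dose Modification lines direct resumption after one held dose for any grade 3 or 4 toxicity. They contain no recovery condition, no exception by event type and no permanent stop, and none appears elsewhere in the visible text. Read literally, this includes reactions that the protocol itself lists for the drug and that can be fatal.

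The size is best given as dose: a ladder that ends at 200 mg/day and not at 0, and between 17 tablets and 1 tablet still directed, depending on when the first event occurs. These counts assume that the 10 days run from the first hydroxychloroquine dose, that the event falls at the end of a day and that the rule is followed exactly. They describe exposure, not harm. No effect on the Day 6 endpoint or on error control is claimed.

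**What to change.** Amend the Dose Modification lines in Section 1.3 A.2 as follows.

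1. Permanently stop hydroxychloroquine, and azithromycin if it is still being taken, for any drug-related grade 4 event and for drug-related ventricular arrhythmia, hypersensitivity or severe skin reaction of grade 3 or higher.
2. For other grade 3 toxicity, keep the twice-daily and once-daily steps, but resume only once the event has resolved or improved to a tolerable grade.
3. Stop after a further grade 3 or 4 episode on once-daily dosing.
4. Name CTCAE 5.0 as the scale, which exclusion 8 already uses.

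The same stop should apply to the blinded tablets in Arms 2 and 3. It should not automatically bar an Arm 3 patient from starting hydroxychloroquine after Day 6, since that patient has taken only placebo. Leave that decision to the investigator, with unblinding if needed. Stopped patients stay in follow-up, give the Day 6 sample and are analysed as randomised. The grade 1 or 2 line can stand.

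The cost is one paragraph in an amendment and a notice to sites, with no new visit, test or sample. A few patients will not complete 10 days of drug, at a rate that the documents do not give. For scale, each 1% of 120 to 160 patients is 1.2 to 1.6 patients. Judgements of recovery may differ between sites, and any unblinding opens the blind for that patient.

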Study participants can receive full supportive care therapies concomitantly during the study. Concomitant therapy includes any prescription medications or over-the-counter preparations used by a patient from ≤ 7 days prior to the first dose of study drug to the end of treatment visit. All concomitant therapy, including vitamins, homeopathic/herbal remedies, nutritional supplements, must be recorded during the screening and treatment period, starting from the date of signature of informed consent, and ending at the End of Treatment (EOT) visit.

B. Subject Enrollment

Patients who are eligible for the study will be enrolled in the clinical trial after they provide informed consent for study participation. A copy of the institution's IRB approved informed consent will be on file at Rutgers Cancer Institute of New Jersey's Office of Human Research Services (OHRS) before any participating institutions may enter patients.

Sites will register and enroll patients through OnCore® the Clinical Trials Management System for this study. Contact the Rutgers Cancer Institute of New Jersey's OHRS Registration Desk [contact] if you have any questions about the Registration/Enrollment process.

- Registration: Any subject that has signed the consent will be entered into OnCore®. A Copy
 of the consent will be uploaded into the Documents section.
- Enrollment: Once eligibility has been confirmed, the completed, signed and dated eligibility
 checklist will be uploaded into the Documents section. OnCore® will randomize the patient
 and a sequence number (subject study ID) will be generated at the time of enrollment, this is
 the point the patient is considered on study.

Patients will not start protocol treatment prior to registration.

C. Study Safety Assessments

The Principal Investigator is responsible for ensuring that all staff involved in the study are familiar with the content of this section.

1. Definitions:

Adverse Events:

An adverse event is the development of an undesirable medical condition or the deterioration of a pre-existing medical condition following or during exposure to a

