Drug Interactions (include but not limited to): Digoxin, Insulin or antidiabetic drugs, Drugs that prolong QT interval and other arrhythmogenic drugs, Mefloquine and other drugs known to lower the convulsive threshold, Antiepileptics, Methotrexate, Cyclosporin, Praziquantel, Antacids and kaolin, Cimetidine, Ampicillin.

Availability: FDA approved; commercially available hydroxychloroquine sulfate will be supplied free of charge to all patients enrolled.

Generic name: Microcrystalline Cellulose

Commercial name: Placebo Source: Commercially available

The placebo for tablet is formulated for oral administration. Placebo tablets are blue, film coated tablets with K20 debossed on one side to match the active formulation. Tablets will be provided in polyvinyl chloride (PVC) / polyethylene (PE) polychlorotrifluoroethylene (PCTFE) film blisters with a paper-backed foil and a secondary wallet for distribution to patients in clinical trials.

Composition:

Component	Standard	Strength (20 mg)	
		Quantity per Unit (mg)	% (w/w)
	Intragranular		
Microcrystalline Cellulose (Avicel PH102)	NF	155.2	97.0%
Croscarmellose Sodium (Ac-Di-Sol)	NF, EP, JP	3.200	2.00%
Magnesium Stearate (non Bovine)	NF, EP	1.600	1.00%
Total	-	160.0	100%
	Top-coat		
Opadry II Blue	Professed	4.800	ca. 3.0%
Purified Water ^b	USP, EP	N/A²	N/A
Purified Water (Packaged) b	USP	N/Aª	N/A

Abbrev = ca., approximately, EP, European Pharmacopeia; NF, National Formulary, JP, Japanese Pharmacopeia

a. Removed during processing.

b. Either Purified Water (USP, EP) or Packaged Purified Water (USP) may be used during processing.

Opadry II Blue contains polyvinyl alcohol (USP, FCC, PhEur, JPE), titanium dioxide (USP, FCC, PhEur, JP), polyethylene glycol [macrogol] (NF, FCC, PhEur, JECFA, JP), talc (USP, FCC, PhEur, JP), FD&C Blue #2 (indigo carmine aluminum lake), FD&C Blue #1 (brilliant blue FCF aluminum lake), and FD&C Yellow #5 (tartrazine aluminum lake).

A.	Drug/Device Accountability and Storage Methods	
	The same of the sa	Marine and American
	Control of the contro	

B. Treatment Compliance

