- 3. Age 18 to 89
- 4. Ability to swallow oral medications
- 5. Patients must read, understand and sign IRB approved informed consent

Exclusion Criteria

- 1. Pregnancy or women who are breast feeding
- 2. Two consecutive negative assays for SARS-CoV-2 infection
- Patients that lack decision-making capacity will not be approached to participate in this study
- 4. Inability to tolerate oral medications
- 5. Allergy or prior adverse reaction to either azithromycin or hydroxychloroquine sulfate
- 6. QTc interval ≥ 470 Msec
- 7. Conditions potentially resulting in drug-induced prolongation of the QTc intervals:
 - a. Congenital or acquired long QTc syndrome
 - b. Family history of sudden death
 - c. History of previous drug-induced QTc prolongation
 - d. Current use of medications with possibly or know risk of QTc prolongation (see Appendix B Drugs associated with a known or possible risk of QTc prolongation)
- 8. History of ongoing ventricular cardiac dysrhythmias of grade 2 as described by NCI CTCAE 5.0 criteria
- 9. History of serious ventricular arrhythmia (VT or VF > 3 beats in a row)

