Appendix B

Drugs associated with a known or possible risk of QT prolongation

[figure not shown]
Drug class	Known risk	Possible risk
ADHD		Atomoxetine
Alpha-blocker		Alfuzosin
Analgesic		Hydrocodone-ER Tramadol
Anesthetic, general	Propofol Sevoflurane	
Anti-androgen		Degarelix Leuprolide
Antianginal	Bepridil	
Antiarrhythmic	Amiodarone Disopyramide Dofetilide Dronedarone Flecainide Ibutilide Procainamide Quinidine Sotalol	
Antibiotic	Azithromycin Clarithromycin Erythromycin Ciprofloxacin Levofloxacin Moxifloxacin	Bedaquiline Gemifloxacin Norfloxacin Ofloxacin Telavancin Telithromycin Lefamulin
Anticancer	Arsenic trioxide Vandetanib Cesium Chloride	Encorafenib Toremifene Dpirubicin Fluorouracil (5-FU) Oxaliplatin Inotuzumab ozogamicin Glasdegib Midostaurin Ribociclib Tamoxifen Eribulin mesylate Lapatinib Osimertinib Capecitabine Sunitinib Bosutinib Dasatinib Nilotinib Bendamustine

Drug class	Known risk	Possible risk
		Sorafenib Ceritinib Entrectinib Necitumumab Cobimetinib Dabrafenib Vemurafenib Tipiracil/Trifluridine Crizotinib Cabozantinib Pazopanib Lenvatinib Vorinostat Tazemetostat Romidepsin Vorinostat Panobinostat Ivosidenib Apalutamide Bortezomib
Anticoagulant		Betrixaban
Anticonvulsant		Ezogabine Felbamate
Antidepressant, SNRI		Venlafaxine
Antidepressant, SSRI	Citalopram Escitalopram	Clomipramine Lithium
Antidepressant, Tetracyclic		Meprotiline Mirtazapine Desipramine Imipramine Nortriptyline Trimipramine
Antiemetic	Ondansetron Droperidol Chlorpromazine	Dolasetron Granisteron Palonosetron Promethazine
Antifungal	Fluconazole Pentamidine	
Antihypertensive		Isradipine Moexipril/hydrochlorothiazide Nicardipine
Antimalarial	Chloroquine Hydroxychloroquine	Arteminol/piperaquine Artemether/Lumefantrine
Antimanic		Lithium

Drug class	Known risk	Possible risk
Antineoplastic		Giltertinib
Antipsychotics	Droperidol Chlorpromazine Haloperidol Pimozide Thioridazine	Perphenazine Promethazine Pimavanserin Asenapine Clozapine Iloperidone Lumateperone Paliperidone Lurasidone Aripiprazole
Antisense oligonucleotide		Nusinersen
Antitubercular		Pretomanid
Antiviral		Efavirenz Lopinavir/Ritonavir Rilpivirine Saquinavir
Antispasmodic		Mirabegron
Cholinesterase inhibitor	Donepezil	
Dopamine agonist		Apomorphine
Estrogen agonist/antagonist		Toremifene
Glucosylceramide synthase inhibitor		Eliglustat
Gonadotropin receptor agonist/antagonist		Leuprolide
Gonadotropin-releasing hormone agonist/antagonist		Degarelix
Histamine H ₂ receptor antagonist		Famotidine

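### The on-study medication rule does not carry forward the QT exclusion or the label warnings, leaving non-assigned azithromycin in Arm 2 and added QT-prolonging drugs without an operative trial rule

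*Protocol*

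**What the plan says.** **On study.** Under Concomitant Medications & Supportive Guidelines, protocol section 1.3 states: "Study participants can receive full supportive care therapies concomitantly during the study". The rest of that text defines concomitant therapy and requires it to be recorded. It names no restricted drug and does not point to the exclusion criteria, Appendix B or section 1.7.

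**At entry.** Exclusion 7d (section 4.1) rules out "Current use of medications with possibly or know risk of QTc prolongation" and refers to Appendix B. The known-risk column of Appendix B includes "Azithromycin Clarithromycin Erythromycin Ciprofloxacin Levofloxacin Moxifloxacin" among antibiotics and "Chloroquine Hydroxychloroquine" among antimalarials.

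**Drug information (section 1.7).** The hydroxychloroquine text says that "hydroxychloroquine sulfate should not be administered with other drugs that have the potential to prolong the QT interval", and its interaction list includes "Drugs that prolong QT interval and other arrhythmogenic drugs". The azithromycin text asks providers to weigh the risk of fatal QT prolongation in at-risk groups, including patients already on QT-prolonging drugs. It adds: "Prescribing azithromycin in the absence of a proven or strongly suspected bacterial infection is unlikely to provide benefit".

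**Blinding.** The placebo is supplied "to maintain the blind between Arm 2 and Arm 3". No azithromycin placebo is described.

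**Monitoring.** Appendix A schedules the ECG at screening only, with daily review of concomitant drugs and adverse events through Day 20. Appendix D asks each day about new medications. SAP section 6.3 requires safety review at least monthly.

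**Arm 3.** In the Arm 3 visit schedule (section 1.3), the stated condition for starting hydroxychloroquine on Day 6 is that symptoms continue.

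**The concern.** The primary comparison, Arm 1 against Arm 2, tests whether adding azithromycin helps, and the outcome is read at Day 6. If Arm 2 patients are prescribed azithromycin before that sample and the drug works, Arm 2 moves towards Arm 1 and the contrast shrinks. Such prescribing is plausible. Nothing described masks azithromycin, inpatients and severe cases are eligible, and the protocol itself presents the combination as promising (6/6 virus-free against 8/14). The 10 extra patients in SAP section 6.1 are for drop-out, so nothing is set aside for this kind of dilution.

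The second issue is safety. The plan treats Appendix B drugs as reason enough to keep a patient out, yet from Day 1 the concomitant-medication rule sets no limit on adding them to hydroxychloroquine. In Arm 3, a listed drug could be started during the placebo days and still be in use when hydroxychloroquine begins, with no stated re-check of 7d.

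**Working it through.** **1. Which text governs a drug started after enrolment?**

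- Exclusion 7d concerns current use at screening. It keeps existing users out but does not govern later starts.
- The concomitant-medication rule allows supportive care and requires a record.
- The dose-modification rules respond to toxicity, not to an added drug.
- Section 1.7 warns, but it is product information. Arm 1 combines the two drugs by design, so the QT statement cannot be applied literally as a trial rule. It also does not reach Arm 3 patients while they take placebo.
- Appendices A and D would reveal an added drug, but neither says what follows.
- SAP section 6.1 has no rule for reporting or handling non-assigned use.

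The position is therefore: warned against in section 1.7, but not made a trial rule.

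**2. Inputs for the power check.** From protocol section 1.5 and SAP section 6.1: 60 patients in each of Arms 1 and 2, virus-free rates 0.571 (Arm 2) and 0.805 (Arm 1), two-sided 5%, uncorrected chi-squared test. Assumed, because the documents give no figure: c, the share of Arm 2 taking non-assigned azithromycin before Day 6, and e, the fraction of the full effect that they obtain.

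**3. Formula.** Power = Φ[(d − 1.96·SE0)/SE1], where d is the difference in rates, SE0 = √[p̄(1 − p̄)·2/60] with p̄ the mean of the two rates, and SE1 = √[p1(1 − p1)/60 + p2(1 − p2)/60].

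**4. Reproducing the plan's figure.** d = 0.234, p̄ = 0.688, SE0 = 0.0846, SE1 = 0.0818. Then (0.234 − 0.1658)/0.0818 = 0.83 and power = 0.798, against the stated 0.80. Exact enumeration of the test gives 0.808.

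**5. Dilution.** Arm 2 rate = 0.571 + 0.234·c·e. For c = 0.20 and e = 1 the rate is 0.6178, so d = 0.1872, SE0 = 0.0827 and SE1 = 0.0809. Then (0.1872 − 0.1621)/0.0809 = 0.31 and power = 0.622.

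| Arm 2 users (of 60) | Full effect | Half effect | Quarter effect |
|---|---|---|---|
| 0 | 0.798 | 0.798 | 0.798 |
| 3 (5%) | 0.759 | 0.779 | 0.788 |
| 6 (10%) | 0.716 | 0.759 | 0.779 |
| 12 (20%) | 0.622 | 0.716 | 0.759 |

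Exact enumeration gives values about 0.01 higher throughout (0.636 in the worst cell). A quarter effect might represent a late start.

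**6. Larger true effects.** With Arm 1 at an assumed 0.85, power is 0.93 with no use. With 20% full-effect use the Arm 2 rate is 0.571 + 0.20·0.279 = 0.6268 and power is 0.80. At the pilot rates (1.00 against 0.571), 20% use leaves power above 0.99.

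**7. No azithromycin effect.** Both arms stay at 0.571 whatever c is, and the rejection rate is the nominal 0.05 (0.053 by exact enumeration).

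**8. Arm 2 against Arm 3** (60 against 30, pooled rate weighted by arm size). At 0.401 against 0.125, power is 0.800. If 3 or 6 of the 30 control patients take non-assigned hydroxychloroquine or chloroquine at full effect, it is 0.69 or 0.56. At the pilot rates (0.571 against 0.125) it goes from 0.995 to 0.975 or 0.92.

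**The case against.** The strongest reply is that the protocol is not silent. Appendix B lists hydroxychloroquine as a known QT risk, so every Arm 2 patient on study drug is in the group for whom section 1.7 urges caution with azithromycin. The hydroxychloroquine warning points the same way, and the treatment plan makes study azithromycin depend on randomisation. That Arm 1 departs from the label by assignment does not cancel the warning for unassigned drugs in Arm 2.

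Much of this stands. A reader might infer that the plan authorises open azithromycin in Arm 2 or leaves it wholly unaddressed, but section 1.7 contradicts that. Nor would any suspected chest infection satisfy the label wording, which calls for proof or strong suspicion. What remains is that these cautions are not turned into an instruction in the one place that governs on-study medication.

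It can also be said that allowing supportive care and analysing as randomised is a legitimate choice with severe inpatients eligible, that only new starts over about six days matter, and that use is already recorded daily. These points limit the likely size. They do not remove the gap, because recording cannot undo exposure before the Day 6 sample and does not say what to do about a QT-prolonging drug.

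Finally, section 4.7 is not fully visible: after the contraception text it breaks off and resumes in privacy items before item F. A rule could sit there, and its absence cannot be asserted.

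**Conclusion.** The point holds in a limited form, with medium confidence, and should be fixed. In the visible text, no operative rule covers non-assigned azithromycin in Arm 2, other Appendix B drugs started on study, or a re-check in Arm 3 before hydroxychloroquine starts.

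For the primary comparison, the cost is a power loss of about 0.04, 0.08 or 0.18 for 5%, 10% or 20% use, if azithromycin works at exactly the planned effect and users obtain all of it. The loss is smaller with partial effect or a larger true difference. The rates of use are assumptions, so a reader should not infer that the trial is in fact underpowered by this amount. Nor is there a route to a false claim of benefit: the dilution is towards no difference, and the type I error stays at its nominal level.

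The safety part rests on the text rather than on arithmetic. A drug class that bars entry is not limited afterwards by the concomitant-medication rule, and no ECG is scheduled after screening. Daily medication and adverse-event review are real safeguards, but they attach no action to an added drug.

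**What to change.** Add to Concomitant Medications in protocol section 1.3:

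> Azithromycin, hydroxychloroquine or chloroquine not assigned by randomisation should not be given before the Day 6 sample unless clinically necessary with no suitable alternative; such use is recorded with its reason. While a participant takes blinded study tablets or hydroxychloroquine, other Appendix B drugs should be avoided where a suitable alternative exists; if one is necessary, the investigator records the reason and decides whether to hold study drug. In Arm 3, criterion 7d is re-checked at the Day 6 medication review, and hydroxychloroquine is not started while an Appendix B drug is in use unless the investigator documents why the benefit outweighs the QT risk.

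Add to SAP section 6.1: report non-assigned azithromycin, hydroxychloroquine or chloroquine use before Day 6 by arm, keeping the primary analysis as randomised.

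The cost is three protocol sentences, one SAP sentence, one table and a recorded reason when a listed drug is needed. No visit or sample is added, and the medication data are already collected daily. The downside is a modest limit on clinicians' choice. Appendix B is broad (it includes ondansetron, famotidine, tramadol and propofol), and the blind extends the advice to Arm 3 patients on placebo, so the wording asks for avoidance rather than imposing a ban. Holding study drug before Day 6 would also cost some assigned exposure.
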